IRB Minimal Risk Protocol Template

General Study Information

Principal Investigator: [name]

Study Title: Seroprevalence of SARS CoV 2 Antibodies in Previously undiagnosed Healthcare Workers

Protocol version number and date: Version 1.0 04/17/2020

Research Question and Aims

Hypothesis: Healthcare workers with suspected COVID-19 exposure and negative test demonstrate seroprevalence of SARS CoV 2 Antibodies.

Aims, purpose, or objectives: To identify healthcare workers with SARS CoV 2 antibodies who have not been previously diagnosed and are presumed COVID-19 negative and determine the level of immunity in this population which could inform further decisions about widespread antibody testing in a healthcare worker population.

Background:

Very little is known about the seroprevalence of SARS CoV-2 Antibodies in a healthcare employee population. Some are recommending antibody testing for healthcare workers on a broad scale to determine immunity. Antibody testing is now available at Mayo Clinic in Florida.

Study Design and Methods

Methods: *Describe in lay terms, completely detailing the research activities that will be conducted by Mayo Clinic staff under this protocol.*

Healthcare workers in surgical and procedural areas will be contacted to participate in this study. Those employees, who were identified as potentially being exposed to COVID-19 and were screened with PCR testing twice (with negative results), will be asked to participate in this study to check for antibodies presence in their blood. Principal Investigator and Co-Investigators will reach out to those employees and offer them participation in this study. A list of employees will be obtained from the Employee Health and Principal Investigator already confirmed that this list will be available as soon as study is approved by IRB.

Upon agreement to participate in this study, the participants will complete a brief survey (attached).

Responses to questions will be directly entered into REDCap and captured by the study team members.

Study participants will be asked to have a blood test for antibodies performed at Mayo Clinic Florida. Approximately 5ml of blood will be obtained for this test. The charge for this test is being covered by the participants' insurance per CARES Act.

Official letter from Mayo Clinic to Medica included in the IRB application. Per email discussion with [name], [name], and [name], the antibodies testing will be paid for by Medica for employees covered by this insurance.

Should results come back with presence of antibodies; the employees will be notified and instructed to follow up with their PCP. The test is not aimed at detecting presence of COVID-19, only antibodies.

Subject Information

Target accrual is the proposed total number of subjects to be included in this study at Mayo Clinic. A "Subject" may include medical records, images, or specimens generated at Mayo Clinic and/or received from external sources.

Target accrual: 300

Subject population (children, adults, groups): Adults

Inclusion Criteria:

- Age \geq 18 years old
- Mayo Clinic employee in procedural and surgical area
- Suspected COVID-19 exposure
- Completed PCR test twice with negative results

Exclusion Criteria:

- Refusal to participate in this study
- Subject not covered by Medica insurance

Biospecimens

Collection of blood samples. When multiple groups are involved copy and paste the appropriate section below for example repeat section b when drawing blood from children and adults with cancer.

- a. **From healthy, non-pregnant, adult subjects who weigh at least 110 pounds.** For a minimal risk application, the amount of blood drawn from these subjects may not exceed 550ml in an 8 week period and collection may not occur more frequently than 2 times per week.

Volume per blood draw: 5 ml

Frequency of blood draw (e.g. single draw, time(s) per week, per year, etc.) single draw

b. **From other adults and children considering age, weight, and health of subject.** For a minimal risk application, the amount of blood drawn from these subjects may not exceed the lesser of 50 ml or 3 ml per kg in an 8 week period, and collection may not occur more frequently than 2 times per week.

Volume per blood draw: ml

Frequency of blood draw (e.g. single draw, time(s) per week, per year, etc.) _____

Prospective collection of biological specimens other than blood: _____

Review of medical records, images, specimens

Check all that apply (data includes medical records, images, specimens).

Only data that exists before the IRB submission date will be collected.

Date Range for Specimens and/or Review of Medical Records:

Examples: *01/01/1999 through 12/31/2015*, or all records through *mm/dd/yyyy*.

Note: The Date Range must include the period for collection of baseline data, as well as follow-up data, if applicable.

The study involves data that exist at the time of IRB submission **and** data that will be generated after IRB submission. Include this activity in the Methods section.

Examples

- The study plans to conduct a retrospective chart review and ask subjects to complete a questionnaire.
- The study plans to include subjects previously diagnosed with a specific disease and add newly diagnosed subjects in the future.

The study will use data that have been collected under another IRB protocol. Include in the Methods section and enter the IRB number from which the research material will be obtained. *When appropriate, note when subjects have provided consent for future use of their data and/or specimens as described in this protocol.*

Enter one IRB number per line, add more lines as needed

Data Specimens Data & Specimens _____

Data Specimens Data & Specimens _____

Data Specimens Data & Specimens _____

Power analyses may not be appropriate if this is a feasibility or pilot study, but end-point analysis plans are always appropriate even if only exploratory. Provide all information requested below, or provide justification if not including all of the information.

Power Statement:

This is an exploratory study and power statement is not applicable at this time.

Data Analysis Plan:

Descriptive statistics and mean, median will be reported for the entire data set. The information will be deducted based on the frequency of identified healthcare workers with demonstrated immunity to COVID-19.

Endpoints

Primary:

Secondary:

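### Does the study need a written exclusion for workers who already had a positive SARS-CoV-2 test?

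*Combined protocol and SAP*

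**What the plan says.** The Study Title reads "Seroprevalence of SARS CoV 2 Antibodies in Previously undiagnosed Healthcare Workers". Under Aims, the target is workers "who have not been previously diagnosed and are presumed COVID-19 negative", and the result is one "which could inform further decisions about widespread antibody testing in a healthcare worker population". The Hypothesis describes the population without mentioning diagnosis: "Healthcare workers with suspected COVID-19 exposure and negative test demonstrate seroprevalence of SARS CoV 2 Antibodies".

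Methods approaches potentially exposed employees who "were screened with PCR testing twice (with negative results", and says of the source of candidates: "A list of employees will be obtained from the Employee Health". After agreeing to take part, "the participants will complete a brief survey (attached".

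The Inclusion Criteria are adult age, employment in a surgical or procedural area, suspected exposure, and "Completed PCR test twice with negative results". The Exclusion Criteria are refusal and lack of cover by the named insurer. Target accrual is 300. The Data Analysis Plan is descriptive and covers all the data collected. The Power Statement calls the study exploratory.

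**The concern.** The title and aim use a stronger term than the criteria deliver. Two negative PCRs do not rule out a third test that was positive. The PCR criterion carries no dates, is not tied to the blood draw, and does not mention other tests. Two kinds of worker therefore meet every listed criterion: one with a positive result at another site, and one who tested positive between the second negative PCR and the draw. No analysis step removes or flags them.

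The study's one product is the frequency of seropositive workers, intended to inform decisions on wider antibody testing. A worker who already knows of an infection is not a case that such testing would uncover. If workers of this kind are more often seropositive than the rest, each one pushes the estimate upward and is reported as an undiagnosed infection.

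A boundary is also left open. A worker diagnosed by a clinician but with only negative tests falls outside the title, yet fits the hypothesis.

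**Working it through.** **Text check.** The places that define the population, side by side:

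| Place | How the population is defined |
|---|---|
| Study Title | previously undiagnosed |
| Aims | not previously diagnosed, and presumed negative |
| Hypothesis | suspected exposure, negative test |
| Methods | potentially exposed, two negative PCRs |
| Inclusion Criteria | suspected exposure, two negative PCRs |
| Exclusion Criteria | nothing on tests or diagnosis |

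None of the six listed criteria (four inclusion, two exclusion) names an earlier positive test, so the literal gap is real. The rows are nevertheless compatible: the aim pairs not being diagnosed with being presumed negative, and two negative PCRs are how the later sections identify presumed negatives.

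**Size, as an illustration.** The plan has no figure to reproduce here, since 300 is given without a power or precision calculation. Only n = 300 comes from the documents. Assumed are the true seroprevalence p in undiagnosed workers (1%, 5%, 10%), the proportion s of already-positive workers who are seropositive (30% to 95%), and their number k.

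- Expected estimate = ((300 − k)p + ks) / 300
- Shift per such worker = (s − p) / 300
- Number at which the shift equals the upper arm = arm × 300 / (s − p), with arm and s − p both in percentage points

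The arm is the distance from the estimate to the upper limit of the exact (Clopper-Pearson) 95% interval.

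| p | Exact 95% interval | Upper arm (points) |
|---|---|---|
| 1% (3/300) | 0.21% to 2.89% | 1.894 |
| 5% (15/300) | 2.83% to 8.11% | 3.113 |
| 10% (30/300) | 6.85% to 13.97% | 3.967 |

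Shift per worker in percentage points, with the first whole number of workers whose combined shift exceeds the arm in brackets:

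| p | s = 30% | s = 50% | s = 80% | s = 95% |
|---|---|---|---|---|
| 1% | 0.097 (20) | 0.163 (12) | 0.263 (8) | 0.313 (7) |
| 5% | 0.083 (38) | 0.150 (21) | 0.250 (13) | 0.300 (11) |
| 10% | 0.067 (60) | 0.133 (30) | 0.233 (18) | 0.283 (15) |

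Example: at p = 1% and s = 80%, 1.894 × 300 / 79 = 7.19, so 8 workers. Check at p = 1%: six workers give (294 × 0.01 + 6 × 0.80) / 300 = 2.58% or, with s = 95%, 2.88%, both inside the interval. Eight workers at s = 80% give 3.11% and seven at s = 95% give 3.19%, both outside.

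At 80% to 95% seropositivity, the thresholds run from 7/300 = 2.3% to 18/300 = 6.0% of the sample. The lower values of s are shown because a worker who tested positive shortly before the draw could be a recent infection, and a high antibody rate should not be taken for granted in that group. At s = 30% the thresholds rise to 20, 38 and 60.

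**The case for a change.** The best argument for a change is that it would be cheap and that small numbers can matter in relative terms. At a true seroprevalence of 1%, three already-positive workers (1% of the sample) would give (297 × 0.01 + 3 × 0.80) / 300 = 1.79%, or 1.94% with s = 95%, nearly double the true value. One eligibility line and at most one survey item would close the gap. Even if the survey asks about earlier tests, nothing in the protocol turns the answer into a rule, and no filter on the Employee Health list is written down.

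The textual point stands, and so does the relative effect at very low prevalence. Neither shows that such workers are present, and the absolute shift in that example is still less than a point, within the sampling uncertainty of an exploratory, descriptive study that tests no threshold.

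The cheap remedy also has a cost. An exclusion for any earlier positive SARS-CoV-2 test would catch a twice PCR-negative worker who had already had a positive antibody test outside the study, which the Background makes possible by noting that antibody testing is available at the site. That worker is arguably the kind the aim seeks. Removing people on an earlier reading of the outcome would pull the estimate down. Excluding clinician-diagnosed workers who have only negative tests would be a further choice that the documents do not settle.

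**Conclusion.** The wording gap is genuine but is missing detail that the rest of the document lets an analyst fill: someone known to have tested positive is neither undiagnosed nor presumed negative, and would not sensibly be reported as such. No change is required.

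The likely effect is small, about 0.07 to 0.31 points per worker for s between 30% and 95% and p between 1% and 10%. At s of 80% to 95%, 7 to 18 such workers among 300 would be needed for the shift to exceed the upper arm of the interval; at lower s, more. These sizes rest on assumed prevalence, seropositivity and counts. The conclusion also allows that the survey and Employee Health list, which are not in the text, may already screen for earlier positives; their absence here is not a fault in the plan.

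Should the protocol be reworded for other reasons, any clarification should concern positive viral tests before the draw and should not exclude on an earlier antibody result. Workers with a clinician diagnosis but no positive viral test can stay in the main result, with the result without them as a sensitivity analysis.

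### Does listing refusal as an exclusion, with no stated participation counts or denominator, require a change to the seroprevalence plan?

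*Combined protocol and SAP*

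**What the plan says.** Under Study Design and Methods, the sampling frame is a register held by the employer: "A list of employees will be obtained from the Employee Health". Recruitment is by invitation: "Principal Investigator and Co-Investigators will reach out to those employees and offer them participation in this study". The same section describes the invitation as one to have blood checked for antibodies. Two steps follow: "Upon agreement to participate in this study, the participants will complete a brief survey", and then "Study participants will be asked to have a blood test for antibodies performed at Mayo Clinic Florida".

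Under Subject Information, the size is given as "Target accrual: 300". The two exclusions are "Refusal to participate in this study" and "Subject not covered by Medica insurance".

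The Data Analysis Plan has two sentences. The first reads "Descriptive statistics and mean, median will be reported for the entire data set". The second bases the conclusions on how often immunity is found among the workers. Neither defines the data set or a denominator, and no section commits to reporting how many workers were listed, invited, willing or tested. The Power Statement calls the study exploratory and gives no precision target.

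**The concern.** Taken literally, the refusal criterion makes a worker who meets all four inclusion criteria but declines ineligible, when that worker is really an eligible non-participant. A report that followed the wording strictly could then show no non-participation among eligible workers, however many had declined.

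That would matter because the result is one proportion with no comparison group in which selection might cancel. The stated aim is to describe immunity in this workforce as a guide to wider testing. Willingness to be tested could be related to past symptoms or perceived exposure, in either direction, and the documents do not say which. Without the number approached, a reader cannot tell a near-complete survey from a half-sample.

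There is also a possible second loss, between survey and blood draw. If the whole data set included people surveyed but not tested, the antibody frequency could be divided by the wrong number.

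**Working it through.** The plan contains no prevalence, precision or participation figure to reproduce, and the target of 300 has no stated derivation. Apart from 300, every input below is an assumption used only to gauge size.

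**1. What the refusal line changes.** Let x be the number positive and n the number with a result. The estimate is x/n. Those who decline are in neither x nor n, whether they are called excluded or non-participating. Deleting the line leaves x/n unchanged.

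**2. How far self-selection could move the estimate.** Let p be the true prevalence and R the participation of seropositive workers relative to seronegative workers. The expected observed proportion is pR / (pR + 1 − p).

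| p | R | Calculation | Observed |
|---|---|---|---|
| 5% | 0.5 | 0.025 / 0.975 | 2.6% |
| 5% | 0.67 | 0.0335 / 0.9835 | 3.4% |
| 5% | 1.5 | 0.075 / 1.025 | 7.3% |
| 5% | 2 | 0.10 / 1.05 | 9.5% |
| 2% | 0.5 | 0.01 / 0.99 | 1.0% |
| 2% | 2 | 0.04 / 1.02 | 3.9% |

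The exact (Clopper-Pearson) 95% interval for 15/300 is 2.8% to 8.1%. For a true 5%, ratios of 0.67 to 1.5 stay inside it. Ratios of 0.5 and 2 fall a little outside.

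**3. What a participation count would tell a reader.** Suppose 15/300 are positive and a fraction f of the eligible workers were tested. If every untested worker were negative, prevalence among all eligible workers would be 0.05f. If every one were positive, it would be 0.05f + (1 − f).

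- f = 0.95: 4.75% to 9.75%
- f = 0.80: 4.0% to 24.0%
- f = 0.50: 2.5% to 52.5%

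These limits ignore sampling error and are extremes. A milder assumption gives non-participants half or twice the participants' 5%. Prevalence in the whole group is then 0.05f + (1 − f) × 0.025 or 0.05f + (1 − f) × 0.10.

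- f = 0.90: 4.75% to 5.5%
- f = 0.70: 4.25% to 6.5%
- f = 0.50: 3.75% to 7.5%
- f = 0.30: 3.25% to 8.5%

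Only the last range reaches past the sampling interval. The count is therefore useful context. It does not alter the estimate, and its worst-case limits are too wide to help where participation is low.

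**4. Denominator.** Suppose 300 are surveyed, 270 tested and 15 positive. Then 15/300 = 5.0% and 15/270 = 5.6%, a difference of 0.6 percentage points. In the Data Analysis Plan, the whole-data-set phrase belongs to the general descriptive summaries, and the antibody frequency is in a separate sentence. Employees are invited specifically to be tested for antibodies, so agreeing to join already implies agreeing to the test. An untested person has no outcome to count. Participants with a result are the reading an analyst would adopt.

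**5. What could be counted.** The numbers listed, agreeing and tested follow from the list and the study's own records. The number invited needs only a note of who was contacted. The number eligible is harder, because "Subject not covered by Medica insurance" is an exclusion and no section says the list records insurance cover. Comparing those who declined with participants would use Employee Health information on people who did not join, and the documents do not show that this is available or permitted.

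**The case for a change.** The best case for a change is that it would be cheap and the omission might be hard to repair. One sentence could commit the team to a participant flow, another could fix the denominator, and a contact log is difficult to rebuild afterwards. The exploratory label does not excuse the silence. It is attached to the power statement, and the protocol template itself says that an analysis plan is appropriate even in exploratory work. With no comparator, the participation rate is one of the few guides a reader has to selection.

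Much of this stands. The plan is silent on both matters, and a good report would give the numbers listed, invited, agreeing and tested, with those tested as the denominator. But nothing in the plan prevents such a report, and none of these additions changes who is recruited, what is measured or the proportion obtained.

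The larger remedies are weaker still. Removing the refusal criterion is a matter of wording. Restating the population adds little, since the eligibility criteria already define it. Counting eligible workers and comparing non-participants depend on data about decliners that the documents do not show the team to hold or be allowed to use.

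**Conclusion.** No change to the plan is called for. Listing refusal as an exclusion is loose wording with no effect on the estimate. The missing counts and denominator are reporting detail that analysts would supply sensibly. Self-selection remains a genuine limit on interpretation, but it follows from voluntary recruitment, and no wording of the criteria would remove it.

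On assumed values, moderate selection (ratios of 0.67 to 1.5 at a true 5%) moves the result by no more than the sampling error of 300 tests. Stronger selection could exceed that error. The denominator choice, with an assumed 10% untested, moves the result by 0.6 percentage points.

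This conclusion rests on two readings: that the antibody frequency is calculated among people with a result, and that the team can give basic recruitment counts from the list it works from. The survey and other application material are not in the documents reviewed, so they could not be checked for further detail.

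### Seroprevalence is to be reported as a bare crude frequency: the missing interval matters whatever the assay, and the missing allowance for assay error matters to a degree the documents do not let us fix

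*Combined protocol and SAP*

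**What the plan says.** The Data Analysis Plan has two sentences. The first is general: "Descriptive statistics and mean, median will be reported for the entire data set". The second is the only one that bears on prevalence: "The information will be deducted based on the frequency of identified healthcare workers with demonstrated immunity to COVID-19". It does not define immunity. The natural reading is a positive antibody result, since Study Design and Methods says "The test is not aimed at detecting presence of COVID-19, only antibodies".

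The Aims under Research Question and Aims contain two purposes. One is identification: "To identify healthcare workers with SARS CoV 2 antibodies who have not been previously diagnosed". The other is estimation: "determine the level of immunity in this population which could inform further decisions about widespread antibody testing in a healthcare worker population". This point concerns only the second.

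Subject Information gives "Target accrual: 300" and, among the inclusion criteria, "Completed PCR test twice with negative results". The Biospecimens section describes a single 5 ml draw. No section supplied names a confidence interval, an assay or cut-off, Se, Sp, a confirmatory test or a misclassification correction. The Power Statement is declared not applicable because the study is exploratory. The template text just above it says "end-point analysis plans are always appropriate even if only exploratory".

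**The concern.** A proportion from at most 300 people carries sampling error that a bare frequency hides. It also mixes true and false positives. Everyone enrolled has two negative PCR results, so low prevalence is plausible, although the documents state no expected value. At low prevalence even a small false-positive rate can make up much of the positive count; at higher prevalence, poor sensitivity pulls the figure down. Since the estimate could inform decisions on wider testing, a reader needs to know how uncertain it is and whether a handful of positives could be assay error alone.

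Timing also matters. If Se and Sp are chosen after the count is known, that choice can move the answer considerably.

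**Working it through.** **Inputs.** From the documents: n = 300 (target accrual), one yes/no result per person, and a crude frequency as the estimator. The plan gives no prevalence, interval or precision figure to reproduce, and no derivation of the 300. All values of Se, Sp and true prevalence p below are assumptions.

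**1. Sampling error alone.** Exact (Clopper-Pearson) 95% intervals need no assay assumption.
- 7/300 = 2.3%: 0.9% to 4.7%
- 15/300 = 5.0%: 2.8% to 8.1%

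**2. Expected crude figure.** crude = p·Se + (1 − p)(1 − Sp). With p = 1% and Se = 90%, the first term is 0.0090 and the second is 0.99 × (1 − Sp).

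| Sp | Expected crude | Exact interval on crude covers true 1% |
|---|---|---|
| 99.8% | 0.0090 + 0.0020 = 1.1% | 98% |
| 99.5% | 0.0090 + 0.0050 = 1.4% | 94% |
| 99% | 0.0090 + 0.0099 = 1.9% | 79% |
| 98% | 0.0090 + 0.0198 = 2.9% | 36% |

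For 0 to 7 positives the exact interval contains 1% (at 7 the lower limit is 0.94%); from 8 it does not. Coverage is therefore the binomial probability of at most 7 positives at the crude rate.

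Bias and coverage should be kept apart. At Sp 99.5% the relative excess is (0.01395 − 0.01)/0.01, about 40%. Coverage stays near 94% only because the interval is wide at this sample size.

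**3. Other prevalences, same four Sp values, Se 90%.** Coverage is 95/84/56/14% at p = 0.5% and 96/97/95/84% at p = 5%.

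**4. The other direction.** With Se 70%, Sp 99% and p = 10%, crude = 0.070 + 0.009 = 7.9%, and coverage is 81%. Even at Se 90% and Sp 99.8%, coverage is 95% at p = 10%, 92% at 15% and 88% at 20%, where crude = 0.180 + 0.0016 = 18.2%.

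**5. Nobody infected.** The chance of 3 or more positives from assay error alone is 2.3/19/58/94% at the four Sp values. Larger counts are not explained this way: 15 or more at Sp 99% has probability 5 × 10⁻⁷.

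**6. Adjustment after the fact.** Rogan-Gladen: adjusted = (crude + Sp − 1)/(Se + Sp − 1). Over Se 70–90% and Sp 98–99.8%, the extremes for 7/300 are:
- Se 90%, Sp 98%: 0.00333/0.880 = 0.4%
- Se 70%, Sp 99.8%: 0.02133/0.698 = 3.1%

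The same range takes 15/300 from 3.4% to 6.9%.

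**7. Carrying the uncertainty in Se and Sp.** Assume validation counts of 90/100 for Se and 495/500 for Sp, and use the Lang-Reiczigel interval for 7/300.
- Point estimate: (0.02333 − 0.01)/0.89 = 1.5%.
- Shrunken inputs: (7 + 1.92)/303.84 = 0.0294; 91/102 = 0.8922; 496/502 = 0.9880.
- Interval centre: (0.02936 + 0.98805 − 1)/0.8802 = 2.0%; half-width 2.4 points.
- Interval: −0.4% to 4.4%.

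For 15/300 the result is 4.5% (1.9% to 8.1%). With 499/500 for Sp, 7/300 gives 2.4% (0.6% to 5.1%).

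**The case against.** The strongest reply is that this is a declared exploratory, minimal-risk study with one binary outcome. Anyone given the positives and the number tested can compute an exact interval and an adjustment later. The plan's reference to descriptive statistics does not bar an interval. The template line on end-point analysis plans does not ask for an interval or a misclassification correction, and the form does contain a descriptive plan. Assay details may also exist in the wider IRB application.

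Much of this stands. A reader might infer that the plan breaches its template; the documents do not support that. The template line shows only that the exploratory label, which is used to waive the power statement, does not also excuse a thin analysis plan. Nor can one infer that the assay is unvalidated or its performance unknown to the team: the analysis plan simply makes no use of such figures. The choice of Lang-Reiczigel is one reasonable option, not a requirement.

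Later correction is possible but is not equivalent to a planned one. Step 6 shows about an eightfold spread for the same 7 positives, although that spread comes from the corners of an assumed grid.

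A fair further objection is that the adjusted interval has little power to exclude 0 where prevalence is low. That is true, and it shapes the wording proposed below.

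**Conclusion.** The omission is certain on the text supplied: the only prevalence estimator is a crude frequency, without an interval and without allowance for assay error. The missing interval should be repaired whatever the assay.

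The size of the assay-error bias is conditional on Se, Sp and true prevalence, none of which is given. Under the assumed Se 90% and true 1%, it runs from slight at Sp 99.8% to nearly threefold at Sp 98% (2.9% against 1%). At Se 90% and Sp 99.8% an ordinary interval is adequate, but only up to about 10% prevalence.

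A reader might go further and infer that the reported seroprevalence must be too high, or that most positives will be false. The documents do not support either. The error can run downwards, larger positive counts could not plausibly be assay error alone at Sp 99%, and with a good assay at low to moderate prevalence the crude result with an interval would serve. The aim of identifying individual workers with antibodies is outside this point. The study is not invalidated; its headline estimate is under-specified, and the repair is cheap if made before results are seen.

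**What to change.** Replace the second sentence of the Data Analysis Plan with:

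> The outcome is antibody positive (yes/no) at the assay's stated cut-off. Positives/tested are reported with an exact 95% interval. Alongside, a Rogan-Gladen adjusted prevalence, (crude + Sp − 1)/(Se + Sp − 1), truncated to 0–1, is reported with a 95% interval that carries the uncertainty in Se and Sp (for example Lang-Reiczigel). Se and Sp, their validation counts and the reference standard for Se are fixed before results are seen. If Se was validated against known past infection, the adjusted figure is labelled as an estimate of past infection, not of antibody presence or immunity. The adjustment is repeated over a range of Se; if validation counts cannot be obtained, it is shown over a stated range of Se and Sp. If the untruncated interval includes 0, the report says that assay error is not ruled out as the source of all positives, that this is not evidence of no infection, and gives the upper limit.

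If Lang-Reiczigel is used, note in the report that its interval is not centred on the point estimate (1.5% against a centre of 2.0% in the 7/300 example).

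Cost: a few lines of text and code, plus the assay's validation counts or a stated range. The price is a wider interval and dependence on validation panels that may not resemble PCR-negative workers, hence the range of Se. Power to exclude 0 is low at low prevalence. In simulation with 300 tested, Se 90% from 100 known positives and Sp 98–99.8% from 200 known negatives (assumed, and fewer negatives than in step 7), the adjusted interval excludes 0 in about 8–10% of studies at true 1%, 21–41% at true 2% and 71–96% at true 5%. That is why the upper limit must be shown.
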